8.2 Reporting of Adverse Events

Adverse Events will be documented according to the Recommended Adverse Event Recording Guidelines for Phase II protocol (see table below).

Recommended Adverse Event Recording Guidelines					
Attribution	Grade 1	Grade 2	Grade 3	Grade 4	Grade 5
Unrelated	Phase I	Phase I	Phase I Phase II	Phase I Phase II Phase III	Phase I Phase II Phase III
Unlikely	Phase I	Phase I	Phase I Phase II	Phase I Phase II Phase III	Phase I Phase II Phase III

Possible	Phase I Phase II	Phase I Phase II Phase III			
Probable	Phase I Phase II	Phase I Phase II Phase III			
Definitive	Phase I Phase II	Phase I Phase II Phase III			

8.3 Reporting Requirements to Supporting Company:

This trial will use the NCI-CTCAE v4.0 criteria for assessment of toxicity and SAE reporting with regard to toxicity grade.

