Most common hematologic adverse events all grades were anemia (31.2%), neutropenia (5%) and thrombocytopenia (11.5%). Most common non-hematologic all grades adverse events occurring in more than 15% of patients were: bone pain, diarrhea, nausea, vomiting and constipation.

Table 1 shows adverse reactions occurring in $\geq 1\%$ of patients and for which the rate for Ra-223 dichloride exceeds the rate for placebo.

System/Organ Class Preferred Term	Ra-223 dichloride (n=600)		Placebo (n=301)	
	All Grades %	Grades 3-4 %	All Grades %	Grades 3-4 %
Blood and lymphatic system disorders				
Thrombocytopenia	11.5	6.3	5.6	2
Neutropenia	5	2.2	1	0.7
Leukopenia	4.2	1.3	0.3	0.3
Pancytopenia	2	1.2	0	0
Gastrointestinal disorders				
Diarrhea	25	1.5 (grade 3 only)	15	1.7 (grade 3 only)
Vomiting	18.5	1.7 (grade 3 only)	13.6	2.3 (grade 3 only)
Nausea	35.5	1.7 (grade 3 only)	34.6	1.7 (grade 3 only)
General disorders and administration site conditions				
Injection site reactions (including erythema, pain and swelling)	1.2	0	0	0

*Adverse reactions are identified using MedDRA version 14.1 and graded according to CTCAE version 3.0.

*An additional clinically important adverse reaction observed in less than 1% of <PTN>-treated patients and at a higher incidence than in placebo-treated patients was lymphopenia (0.8% vs. 0.3%).

Secondary Malignant Neoplasms

No cases of radiation-induced cancer have been reported in reported in clinical trials with radium-223 dichloride in follow-up of up to three years. However, the radiation dose resulting from therapeutic exposure may result in higher incidence of cancer (e.g. sarcomas of the bone, or leukemia), mutations and a potential for development of hereditary defects.

2. Study objectives

Primary Objective:

- To identify markers of both predictive and prognostic importance within bone marrow biopsies, aspirates as well as serum in patients with metastatic CRPC to bone, to be treated with the standard 6 doses of Alpharadin.

[figure not shown]
Secondary Objectives:

- Link PSA initial concentration (as defined within PCWG2) to modulation of bone markers, in the blood, urine and bone marrow plasma of study patients
- Estimate the efficacy and PFS by PCWG2 in study patients
- Develop a deeply annotated tissue repository for later hypothesis generating associations
- Correlative studies in prostate cancer patient-derived mouse models to validate predictive and prognostic biomarker associations (SEE APPENDIX E)

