4.1 Inclusion criteria

1. Histologically proven adenocarcinoma of the prostate with evidence for skeletal metastases on bone scan and/or CT scan.
2. Eastern Cooperative Oncology Group (ECOG) performance status < 2. (Karnofsky Performance Status $\geq 50\%$)
3. Serum testosterone levels $< 50\text{ng/ml}$
4. Ongoing gonadal androgen deprivation therapy with LHRH analogues or orchiectomy. Patients, who have not had an orchiectomy, must be maintained on standard dosing of LHRH analogue therapy at appropriate frequency for the duration of the study
5. Life expectancy of at least 12 weeks (3 months).
6. Discontinue any steroids prescribed to specifically treat prostate cancer (for e.g as a secondary hormonal manipulation or for cord compression) > 4 weeks prior to study drug. Steroids chronically prescribed for a non-cancer-related illness (e.g. asthma or COPD) that is well controlled with medical management are permissible to an equivalent of < 10 mg Prednisone daily. Note: Steroids may be administered during the study as supportive care.
7. Laboratory Requirements:
 - a. WBC count $> 3,000/\mu\text{l}$
 - b. Absolute Neutrophil Count (ANC) $> 1,500/\mu\text{l}$
 - c. Hemoglobin $\geq 8.0 \text{ g/dL}$ independent of transfusion
 - d. Platelet count $\geq 100,000/\mu\text{L}$
 - e. Serum albumin $\geq 3.0 \text{ g/dL}$
 - f. Calculated or measured creatinine clearance $> 30 \text{ mL/min}$
8. All acute toxic effects of any prior treatment have resolved to NCI-CTCAE v4.0 Grade 1 or less at the time of signing the Informed Consent Form (ICF).
9. Patient must be willing and able to comply with protocol requirements. All patients must sign an informed consent indicating that they are aware of the investigational nature of this study.
10. Patients must also have signed an authorization for the release of their protected health information.

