7.2 Evaluations During Study

On-study tests/visits that must occur within a defined time frame will have a standing window of allowance that is equal to +/- 7 days.

	Screening	Every 4 weeks	Week 12 only	Safety FU visit (Week 24)	Long-term Follow-up
Medical History	x ^a				
Physical Exam	x ^a	x		x	
Vital Signs ⁱ	x ^a	x ^e		x	
ECOG PS	x ^a			x	
Weight	x ^a			x	
CBC/ diff. and plt.	x ^a	x ^e		x	
Serum Chemistry	x ^{a, c}	x ^c		x ^c	
Urinalysis					
PT/PTT	x ^a				
PSA	x ^a	x		x	
Testosterone	x ^a			x	
ECG	X ^a				
ECHO ^j	X ^a				
Chest X-ray	x ^b				
Na-Fluoride PET/CT whole body	x ^b			x	
Bone Scan	x ^a				
Monitor Adverse Events	<----->				
Concomitant Medications	<----->				
Bone marrow asp/bx	x ^a		x	x	
Survival Follow-up					x ^d
Optional Procedures					
Blood for Correlative Studies	x			x	
Urine for Correlative Studies	x			x	

a. Within 21 days of registration

- b. Within 6 weeks of registration
- c. Serum chemistries including albumin, alkaline phosphatase, ALT, AST, calcium, LDH, total bilirubin, creatinine, magnesium, phosphate, calcium, electrolytes (sodium, potassium, chloride, CO₂)
- d. Patients will be followed for survival every 6 months after completion of therapy. This may be done by phone call, e-mail, or medical record review.

8. Adverse Event Reporting

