10.3 Descriptive Statistics

Patient demographics and medical status at study enrollment will be tabulated for all enrolled patients. Descriptive plots and summaries of adverse events (AE), PD measures, as well as

serum and bone marrow biomarkers will be presented. The proportions of patients with at least a 30% increase or decrease in any marker will be presented. AEs will be reported by grade and relationship to study interventions (therapy and blood draws and biopsies all constitute study interventions).

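### All-grade cytopenia rates can be understated, mainly for anaemia: section 8.2 leaves out grade 1–2 events judged unrelated or unlikely, and the scheduled blood counts have no planned analysis

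*Combined protocol and SAP*

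**What the plan says.** Section 8.2 sets the recording rule: "Adverse Events will be documented according to the Recommended Adverse Event Recording Guidelines for Phase II protocol". The grid that follows crosses attribution with grade and names the trial phases that record each cell. The two lowest attribution rows begin "Unrelated Phase I Phase I Phase I Phase II" and "Unlikely Phase I Phase I Phase I Phase II". Grades 1 and 2 are thus marked for phase I only, and phase II enters at grade 3. The next row begins "Possible Phase I Phase II", so low-grade events judged at least possibly related are recorded here.

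The schedule in section 7.2 has a row for "CBC/ diff. and plt", with entries at screening, every 4 weeks and at the week 24 safety visit. Section 10.2 lists no haematology variable. Section 10.3 promises descriptive summaries of adverse events, pharmacodynamic measures and biomarkers, and says that "AEs will be reported by grade and relationship to study interventions". Sections 10.3 to 10.6 give no worst grade, shift table, nadir or time course for haemoglobin, neutrophils, platelets or white cells. Section 8.3.1 counts laboratory tests as part of AE monitoring but adds no analysis of them.

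Section 10.7 has a separate Bayesian toxicity rule, based on events of grade 3 or higher that are at least possibly related to study drug.

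**The concern.** The AE table has two dimensions, grade and relationship, and the recording rule empties one corner of it. The grade 1–2 cells under unrelated and unlikely will hold nothing because nothing was collected, yet a reader may take them as zero events. Any all-grade rate summed from that table omits whatever fell into those cells, so the error can only be downward.

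Cytopenias are especially exposed. There is no control arm, the men have bone metastases, and entry is allowed with haemoglobin as low as 8.0 g/dL, so a mild fall can reasonably be put down to the disease. Such a fall leaves no AE record, although the count itself is in the database and no planned table uses it.

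At stake is the descriptive account of low-grade haematological toxicity when a marrow-irradiating drug is given with repeated marrow biopsies, and any comparison with the all-grade rates that section 1.4 quotes for the drug.

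**Working it through.** **1. The plan's own safety figures.** The section 10.7 boundaries follow from stopping when P(Beta(1+x, 1+n−x) > 0.20) > 0.95, for x patients with toxicity out of n evaluable. For x = 3 to 8 the largest such n is 6, 9, 13, 16, 20 and 24, as in Table 10.7.1; 9 of 25 gives a posterior probability of 0.977. Monitoring after each patient from the fifth gives early-stopping probabilities of 0.023, 0.084, 0.206, 0.381, 0.683 and 0.871 at true rates 0.10, 0.15, 0.20, 0.25, 0.33 and 0.40, in agreement with Table 10.7.2. The rule uses only events of grade 3 or higher, and section 8.2 records these whatever their attribution. The recording filter does not touch it.

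**2. Inputs for the all-grade rates.** Table 1 in section 1.4 gives all-grade and grade 3–4 rates on Ra-223. The grade 1–2 rate is the difference, assuming no grade 5 cytopenias. Let f be the share of grade 1–2 events judged unrelated or unlikely. The documents give no value; 0.25–0.75 is an assumption, with f = 1 as the extreme.

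**3. Formulas.**
- Recorded all-grade rate = grade 3–4 rate + (1 − f) × grade 1–2 rate.
- Expected patients lost = 25 × f × grade 1–2 rate.
- Chance of losing at least one = 1 − (1 − f × grade 1–2 rate)^25.

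| | All grades | Grade 3–4 | Grade 1–2 | Recorded, f = 0.25 / 0.75 / 1 | Patients lost of 25, f = 0.25 / 0.75 / 1 | Chance of ≥1 lost, f = 0.25 / 0.75 / 1 |
|---|---|---|---|---|---|---|
| Thrombocytopenia | 11.5% | 6.3% | 5.2% | 10.2 / 7.6 / 6.3% | 0.3 / 1.0 / 1.3 | 28 / 63 / 74% |
| Neutropenia | 5% | 2.2% | 2.8% | 4.3 / 2.9 / 2.2% | 0.2 / 0.5 / 0.7 | 16 / 41 / 51% |
| Leukopenia | 4.2% | 1.3% | 2.9% | 3.5 / 2.0 / 1.3% | 0.2 / 0.5 / 0.7 | 17 / 42 / 52% |

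**4. Anaemia.** Section 1.4 gives 31.2% at all grades (25 × 0.312 = 7.8 patients) and no grade split, so the split is a second assumption.
- If half is grade 1–2 (15.6%), the loss is 25 × 0.25 × 0.156 = 1.0 to 25 × 0.75 × 0.156 = 2.9 patients, and the chance of losing at least one is 63–96%.
- If a quarter is grade 1–2 (7.8%), the loss is 0.5–1.5 patients.
- If all is grade 1–2, the loss is 2.0–5.9 patients.

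**5. Is attribution to disease plausible?** On placebo, grade 1–2 thrombocytopenia was 5.6 − 2 = 3.6%, against 5.2% on drug, so a background share of 3.6/5.2 = 69% is conceivable. Dropping that share would leave 11.5 − 3.6 = 7.9% recorded, with 25 × 0.036 = 0.9 patients lost. For neutropenia the placebo figure is only 1 − 0.7 = 0.3%, against 2.8% on drug, and for leukopenia it is 0.3 − 0.3 = 0%, against 2.9%. The background argument is therefore weak for those two. Anaemia does not appear in Table 1, which is restricted to reactions more frequent than on placebo. If that table is complete, anaemia is the cytopenia most easily assigned to the disease.

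**The case against.** The strongest reply is that nothing the trial sets out to learn depends on an all-grade cytopenia rate. The objectives concern biomarkers, PFS, OS and a tissue repository, and section 10.8 treats the work as observational and preliminary. That stands, and it keeps the point low in severity.

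The size is also small beside sampling error. The binomial standard error of 11.5% at n = 25 is √(0.115 × 0.885 / 25) = 6.4 percentage points, against an assumed bias of 1.3–3.9 points for thrombocytopenia. That stands too, although a one-directional omission is worth removing when the data are already held.

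A reader might infer that the rates will certainly be understated. The documents do not support this. Section 6 itself warns of treatment-related haematology changes, section 8.3.1 points investigators to the drug's expected effects, and a low-grade fall judged possibly related is recorded.

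A reader might also infer that the plan names myelosuppression as the drug's main harm. It does not. Thrombocytopenia has the highest grade 3–4 rate in Table 1, but at all grades nausea (35.5%) and diarrhea (25%) exceed every cytopenia listed there.

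Nor is the AE table the only safety output. Section 10.7 has the stopping rule and a 9-of-25 criterion for judging repeated biopsies during therapy too toxic.

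Finally, laboratory grades have their own faults. In a single arm they include disease-related falls. Transfusion, erythropoietin and growth factors, all allowed on study, can raise counts. Values every 4 weeks can miss a nadir. Nor would they match Table 1 in method, since that table is AE-based under CTCAE v3.0. These points stand, and they are why the laboratory summary should supplement the AE table rather than replace it.

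**Conclusion.** The point holds as a gap in descriptive safety reporting. A stated recording rule, combined with the absence of any analysis of the counts, means that all-grade cytopenia rates can be biased downward and cannot be biased upward by this route. Anaemia is the most exposed, at about 1–3 patients of 25 if half of it is low grade and 25–75% of that is judged unrelated or unlikely. Thrombocytopenia comes next, at about one patient or fewer under the same attribution range. For neutropenia and leukopenia the expected loss is about half a patient or fewer, and below one patient even if every low-grade event is dropped.

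These sizes rest on three assumptions: the attribution share, the anaemia grade split, and the carry-over of AE-based phase III rates to this trial. The direction rests only on sections 8.2 and 10.3. Rates for grade 3 and higher events, the stopping boundaries and the final toxicity criterion need no change on this account. The change is a cheap improvement, not the repair of a planned conclusion.

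**What to change.** Add to section 10.3, beside the AE table:

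- A descriptive table of worst post-dose CTCAE v4 grade against baseline grade for haemoglobin, neutrophils, platelets and white cells, with a plot of change from baseline by cycle.
- Its source: all available blood counts, scheduled and unscheduled, in patients who received at least one dose, regardless of attribution. Note that this population differs from the section 10.1 toxicity set, which is defined by having had a marrow biopsy.
- A flag on values obtained after transfusion or growth-factor use.
- A footnote to the AE table saying that grade 1–2 events judged unrelated or unlikely were not collected, so those cells are not zeros.

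The cost is a few sentences, one table and one plot; the scheduled counts are already collected, and no new visits are needed. The downside is that the laboratory rates will look somewhat higher because they include disease-related falls; the text should say so.

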8.3.1 Adverse events

Investigators should refer to the Safety Information section of the current IB for Ra 223 dichloride, including the DCSI (development core safety information), for the expected side effects of Ra 223 dichloride. As with any agent, there is always the potential for unexpected AEs, including hypersensitivity reactions. The IB will be updated if any new relevant safety data are obtained.

Therapeutic monitoring should be performed following dose selection of Ra 223 dichloride in a manner consistent with the local clinical standard of care. In general, subjects should be closely monitored for side effects of all concomitant medications regardless of the path of drug elimination.

All concomitant medications must be recorded in the subject's source documentation. Subjects must be carefully monitored for AEs. This monitoring also includes clinical laboratory tests. Adverse events should be assessed in terms of their seriousness, intensity, and relationship to the study drug, or other chemotherapy/treatment.

8.3.2 Reporting of serious adverse events

Each serious adverse event must be followed up until resolution or stabilization, by submission of updated reports to the designated person. An isolated laboratory abnormality that is assigned

grade 4, according to CTC definition, is not reportable as an SAE; unless the investigator assesses that the event meets standard ICH criteria for an SAE. CTC grade 4 baseline laboratory abnormalities that are part of the disease profile should not be reported as an SAE, specifically when they are allowed or not excluded by the protocol inclusion/exclusion criteria.

All serious adverse events should be reported to Bayer within 24 hours. In the event of such an event, the investigator should refer to the Pharmacovigilance section of the contract for reporting procedures.

The Investigator may report serious adverse drug reactions (SADRs) using the MD Anderson Adverse Event Form.

All reports shall be sent electronically to:

Electronic Mailbox: [contact]

Reports for all Bayer products can also be phoned in via our Clinical Communications Dept:

[contact]

8.3.4 Progressive disease

If progressive disease leads to signs and symptoms that meet the criteria for an SAE (i.e., hospitalization, disability, death, or important medical event), the signs and symptoms should be reported as an SAE and not the underlying progressive disease.

Death

If any subject dies during the trial or within 30 days of the end-of-treatment visit, the investigator will inform Bayer and record the cause of death in detail (using the SAE Form) within 24 hours.

9. Withdrawal of subjects from study

Subjects must be withdrawn from the trial (treatment and procedures) for the following reasons:

- Subject withdraws consent from study treatment and study procedures. A subject must be removed from the trial at his/her own request or at the request of his/her legally acceptable representative. At any time during the trial and without giving reasons, a subject may decline to participate further. The subject will not suffer any disadvantage as a result.
- Subject is lost to follow-up.
- Death.

Subjects may be withdrawn from the study for the following reasons:

- The subject is non-compliant with study drug, trial procedures, or both; including the use of anti-cancer therapy not prescribed by the study protocol.
- If, in the investigator's opinion, continuation of the trial would be harmful to the subject's well-being.
- The development of a second cancer.
- Development of an intercurrent illness or situation which would, in the judgment of the investigator, significantly affect assessments of clinical status and trial endpoints.
- Deterioration of ECOG performance status to 4.
- Use of illicit drugs or other substances that may, in the opinion of the investigator, have a reasonable chance of contributing to toxicity or otherwise skewing trial result.

Any subject removed from the trial will remain under medical supervision until discharge or transfer is medically acceptable.

In all cases, the reason for withdrawal must be recorded in the CRF and in the subject's medical records.

9.1 Screen Failures/Dropouts

A subject who discontinues study participation prematurely for any reason is defined as a “dropout” if the subject has already been randomized; assigned to treatment/run-in/wash-out; administer at least one dose of study drug.

A subject who, for any reason (e.g. failure to satisfy the selection criteria), terminates the study before the time point used for the definition of “dropout” (see above) is regarded a “screening failure”.

9.2 Replacement

No withdrawn subjects will be replaced.

10. Statistical Considerations

10.1 Analysis sets

Full population:

All enrolled patients will be used for demographic reporting and calculations of the numbers of patients able to complete the planned schedule and be evaluable for serum and bone marrow marker studies.

Evaluable for Serum Markers:

All patients who have usable baseline and at least one post-baseline serum draws will be evaluable for analysis of serum markers.

Evaluable for Bone Marrow Markers:

All patients who have usable baseline and at least one post-baseline bone marrow biopsy will be evaluable for analyses of bone marrow markers.

Toxicity:

All patients who receive a bone marrow biopsy will be evaluable for toxicity.

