10.2 Variables

Overall survival (OS):

OS will be measured as the number of months from enrollment until death. Patients who are alive at the time of database lock will be censored on the date of last contact.

Progression-free survival (PFS):

PFS will be measured as the number of months from enrollment until progression or death, whichever comes first. Patients who are alive and free of progression at their last response evaluation will be censored on that date. Progression will be defined by the standards set forth within PCWG2.

Demographic variables:

Age at enrollment, race, ethnicity, ECOG status, extent of bone disease (< 6, 6-20, >20)

PD Effects:

Tumor/osteoblast/osteoclast, Ki-67, gamma H2AX, cleaved PRP, cytokeratin/PSA, BALP, and TRAP

Serum biomarkers:

ALP, BALP, APG, RANKL, OPN, OC, CTX, PINP

Bone marrow biomarkers:

Alkaline phosphatase, osteocalcin, DMP, sclerostin, tenascin, periostin, lumican, decorin, osteopontin, osteonectin, nidogen-1, TGFb-induced protein ig-h3.

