10.4 Markers

Markers will be measured repeatedly over time. Any patient with both baseline and at least 1 later measurement will be included in descriptions of each marker. Patients will also be classified for each marker based on whether the marker decreased by at least 30%, stayed with 30% of baseline, or increased by at least 30%. Currently there is no knowledge of how the planned PD, serum, and bone marrow markers may predict overall survival. Exploratory analyses described below will be performed on the continuous values of the markers, changes, in the markers as continuous measures, and the classification strategy described here.

16.3.3 Survival Analysis.

Overall (OS) and progression-free (PFS) survival will be calculated from the date of study enrollment and will include all enrolled patients. Survival analyses will be performed when 90% of patients have died or 2 years after the last patient has completed treatment, whichever comes first. Plots of all patients and subgroups identified by marker exploration (described below) will be presented using the methods of Kaplan and Meier.

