10.5 Primary Objective Exploration

Each marker will be tested individually using a Cox regression model to determine whether it is associated with overall survival. Markers measured on a continuous or ordinal scale will be included with their original units in the model. First, the baseline values will be used to determine if the baseline is associated with survival. Next we will calculate the percent change from baseline and use that as a continuous measure in the model. The ordered category of reduced by 30%, same, or increased by 30% grouping will be used in the model. Finally, all observed values of the marker will be included as a time-varying covariate in the Cox regression model. Since this is an observational study to identify potential usefulness of biomarkers in predicting overall survival, no formal adjustments for multiple testing will be needed for future trial planning. However, for publication, only markers with a significance level of ≤ 0.002 will be considered meaningful in predicting survival. This is based on a Bonferroni correction of approximately 25 markers of interest. Additional regression-tree style partitioning may be performed to identify potentially meaningful cutpoints for combinations of markers. Cutpoints will be examined together with demographic and medical status variables. This will be purely exploratory and will need to be confirmed in an independent data set in a future trial.

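### Section 10.1 requires a post-baseline sample for every marker analysis, although the baseline-marker Cox model in 10.5 needs only the baseline value; the sections should be reconciled so that early deaths and dropouts stay in that model

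*Combined protocol and SAP*

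**What the plan says.** Section 10.1 defines one set per specimen. For blood: "All patients who have usable baseline and at least one post-baseline serum draws will be evaluable for analysis of serum markers". For marrow: "All patients who have usable baseline and at least one post-baseline bone marrow biopsy will be evaluable for analyses of bone marrow markers". Neither sentence makes an exception, and no set is defined for patients who have only a baseline sample. The full population is assigned to demographic reporting and to counting who completes the schedule and is evaluable.

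Section 10.5 then fits a series of Cox models for each marker: baseline value, percent change, the 30% categories, and all observed values as a time-varying covariate. On the first it says: "First, the baseline values will be used to determine if the baseline is associated with survival". It names no analysis set for any of them. Section 10.6 applies similar analyses to progression-free survival.

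Two other texts bear on the question. Section 10.4 gives the two-sample rule a narrower scope: "Any patient with both baseline and at least 1 later measurement will be included in descriptions of each marker". The paragraph numbered 16.3.3, between 10.4 and 10.5, says of OS and PFS that they "will be calculated from the date of study enrollment and will include all enrolled patients". Section 10.2 sets the time origin: "OS will be measured as the number of months from enrollment until death".

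**The concern.** A baseline prognostic model needs a baseline value and a survival time. If 10.1 governs it, entry also depends on something that happens later: living to, and giving, a repeat sample. Patients who die early have informative survival times, and they would be removed although their marker value is already in hand. The result would then describe patients who reached a repeat sample, not patients starting treatment.

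With 25 patients and no replacement of withdrawn subjects (9.2), each lost event counts. The sample-size statement in 10.8 makes no allowance for non-evaluable patients. An analyst could also follow either 10.1 or the all-enrolled sentence and report a different n for a primary-objective model. That choice should be settled before data are seen.

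**Working it through.** **Inputs from the documents**
- 25 patients, HR 1.57 per unit, marker SD 1.25, two-sided 5%, 80% power; second scenario HR 1.45 with SD 1.5 (10.8).
- First repeat marrow at week 12 (Section 3 and the 7.2 table). Blood panel repeated at week 12 in Section 3; in the 7.2 table, correlative blood is next marked at week 24, among optional procedures. Alkaline phosphatase is also in the 4-weekly chemistry (7.2).
- Median OS 14.9 months in the phase III radium arm (1.3). Section 10.8 assumes no median.
- Life expectancy of at least 12 weeks required (4.1, criterion 5).

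**Assumptions:** exponential survival; all remaining patients die before analysis. The documents give no dropout or missed-sample rate.

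**Step 1: reproduce 10.8.** Events needed for a continuous covariate: D = (1.960 + 0.842)² / (SD × ln HR)².
- HR 1.57, SD 1.25: 7.849 / (1.25 × 0.4511)² = 7.849 / 0.3179 = 24.7, so 25 events. Power at 25 events = Φ(√25 × 0.5638 − 1.960) = Φ(0.859) = 80.5%.
- HR 1.45, SD 1.5: 25.3 events; power at 25 events 79.6%.

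The plan's figure reproduces, but only with all 25 patients in the model and all 25 dead.

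**Step 2: deaths before a repeat sample.** P = 1 − 2^(−t/14.9), t in months.
- Week 4, t = 0.92: 4.2%, about 1 of 25 (relevant to ALP if the routine draws count).
- Week 12, t = 2.76: 12.0%, about 3 of 25.
- Week 24, t = 5.52: 22.6%, 5.7 of 25, or about 6.

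For medians of 11.3, 18 and 24 months, the expected deaths are 3.9, 2.5 and 1.9 before week 12, and 7.2, 4.8 and 3.7 before week 24.

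**Step 3: effect on the baseline model.** Power = Φ(√D × 0.5638 − 1.960).

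| Patients excluded | Events | Power, HR 1.57 | HR detectable with 80% power |
|---|---|---|---|
| 0 | 25 | 80.5% | 1.57 |
| 1 | 24 | 78.9% | 1.58 |
| 2 | 23 | 77.2% | 1.60 |
| 3 (week 12) | 22 | 75.3% | 1.61 |
| 4 | 21 | 73.4% | 1.63 |
| 5 | 20 | 71.3% | 1.65 |
| 6 (week 24) | 19 | 69.1% | 1.67 |

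If the analysis is triggered at 90% dead (22.5, so 23 deaths), power is 77.2% with nobody excluded, 71.3% with 3 early deaths excluded and 64.2% with 6.

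**Step 4: bias.** After the repeat-sample time, the risk sets are the same whether or not earlier deaths were ever included, so under proportional hazards their removal should not shift the estimate. A simulation with 1,000 patients per run agrees: HR 1.56 with and without the week-12 exclusion, and 1.57 with and without the week-24 exclusion.

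**The case against.** The strongest reply is that the plan never says the baseline model uses the 10.1 sets. Section 10.5 names none, 10.4 ties the two-sample rule to descriptions, and 16.3.3 includes all enrolled patients. On that reading nobody with a baseline value is lost. This stands in part: exclusion is what 10.1 says if applied, not something 10.5 states. It does not remove the point, because 10.1 speaks of marker analysis without limit, and 16.3.3 concerns the calculation of OS and PFS and does not say it overrides the marker sets.

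A reader might infer that every patient who declines the week-12 biopsy disappears. The text does not support that. The sets are specimen-specific, so refusing a biopsy leaves the serum set untouched, and any one later sample is enough, so a week-24 sample restores a patient who missed week 12.

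A reader might also infer a much larger loss of power. A simulation with 25 patients and a Wald test gives 66% falling to 57% (week 12), and 67% falling to 48% (week 24). Those runs start well below the 80% in 10.8, because they do not use the large-sample formula behind that figure. The drop on the plan's own basis is about 5 or 11 points. The week-24 case concerns correlative blood only, and only if the 7.2 table prevails over Section 3.

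Finally, the marrow set is keyed to a biopsy, and one might infer that a usable aspirate with a failed core is discarded for all 12 marrow factors. Section 3 expressly describes only four of them as aspirate factors, and the 7.2 table schedules aspirate and biopsy as one procedure. This merits a clarifying word, no more.

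**Conclusion.** The point holds as an unreconciled rule with a moderate cost. Followed literally, 10.1 removes about 3 of 25 patients from the baseline model when the first repeat is at week 12, and up to about 6 when it is at week 24. Power for HR 1.57 falls from 80.5% to about 75% or 69%. The counts rest on an exponential curve and a median taken from the phase III trial. They lean high because of the 12-week life-expectancy criterion; refused samples and dropouts would add losses at a rate the documents do not give. For ALP the loss may be about 1 patient.

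It is tempting to say that the hazard ratio itself would be biased. The documents do not support that as a general claim: bias needs a marker effect concentrated early, or a selected group among those who survive but give no repeat sample. What is certain, if 10.1 is applied, is fewer events and a narrower population. Since the plan calls its findings preliminary, this should be fixed but does not undermine the study.

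**What to change.** - State in 10.1, 10.5 and 10.6 that the baseline-marker Cox models include every enrolled patient with a usable baseline value of that specimen.
- Say the same for the time-varying model, where a patient with only a baseline value can still contribute follow-up.
- Keep the requirement for a post-baseline sample in the percent-change and 30%-category models and in the marker descriptions of 10.4.
- Reconcile 10.1 with the all-enrolled sentence under 16.3.3, and report n and events for each model.
- As a secondary clarification, say for each marrow factor whether evaluability depends on the aspirate or the core.

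The cost is wording only: no added patients, visits or samples. The downside is that n will differ between models for the same marker, which reporting n makes plain.
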